### **2.7 Accrual**

One hundred depressed participants will be recruited from the community, from outpatient psychiatry clinics at the University of Pennsylvania (General Outpatient Psychiatry, Family Medicine, Geriatric Psychiatry, the Treatment Resistant Depression Clinic, the HUP consult liaison services), and from the Veterans' Administration Medical Center to complete this study with usable data. Fifty non-depressed control participants will also be recruited from the community and the aforementioned sources to complete this study with usable data.

Careful consideration was provided to the determination of sample size requirements. The following section breaks down the statistical methods and theoretical justification for our sample size of 150 participants: 100 depressed (High and Low CRP groups) and 50 control.

Aim 1: Characterize neuroanatomical and neuropsychological effects of abnormal cytokines in MDD. Hypothesis 1a: Inflammatory cytokines will be elevated centrally and peripherally relative to matched controls; neuropsychological performance will be poorer in MDD; hippocampus, amygdala and PFC volumes will be decreased in MDD; and connectivity of hippocampus and amygdala to rostral AC and DLPFC will be decreased in MDD. The power for the IL-6 mean differences was based on our preliminary IL-6 data where the mean (SD) difference is 2.1 (3.6), with 80% power, two-tailed t-test at 5% significance level. A t-test was used to estimate the power to compare the mean difference of regional correlations (functional connectivity) and neuropsychometric function between controls and depressed subjects. To achieve 80% power

CONFIDENTIAL

with a two-tailed test and 5% significance level, an effect size (mean difference/SD) of at least .49 can be detected for a sample of 150 subjects, where 50 are controls. Based on our preliminary data, the group difference of the mean (SD) Fisher-z of the amygdala-subgenual AC is 0.23 (0.17), and of hippocampus-DLPFC is -0.24 (0.12). The preliminary neuropsychometric data supports this power analysis and requires a group difference of the mean (SD) for episodic memory of -1.44 (2.96) and for executive function of -1.64 (3.35).

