## **6 Analysis Plan**

### **6.1 Data Analysis and Predictions**

At a basic level, the design of this trial is simple repeated measures design with a) two replicates (time points) b) baseline covariates and outcomes, and c) a single between-person factor (initial case-control depression status). The data collected at two time points to be included in analysis (pre- and post-treatment) will be the depression severity, inflammatory markers, resting state functional connectivity and neuropsychometric data. There have been no published studies to date examining adjuvant celecoxib and SSRI treatment in patients who simultaneously received assessment of inflammatory biomarkers. However, based on our own small pilot sample we will have greater than 85% power to detect differences in changes in IL-6 between SSRI responders and SSRI + celecoxib responders. Volumetric data and confounders to be included in the analysis will be collected at baseline. Classic models of change scores can be used where the baseline level can be controlled giving the so-called residual change score. Use of residualized change scores has several analytic advantages: (1) control for variance (the best predictor of today's value is yesterday's value), (2) statistically each subject is started at the same point. Thus, our estimation model will be extended from the classic model of change scores to a repeated measures ANOVA (analysis of variance) or mixed model repeated measures design. A joint modeling approach with mixed models for repeated measures data can be used to address within-subject variation and between-subject variation of the repeated measurements of multiple

CONFIDENTIAL

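### Section 6.1 presents residualised change as starting every subject at the same point; if used for depressed versus control, it would show a difference in change when neither group has changed

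*Combined protocol and SAP*

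**What the plan says.** Section 6.1 describes a design with two time points and "a single between-person factor (initial case-control depression status"). It lists depression severity, inflammatory markers, resting state connectivity and neuropsychometric data as the outcomes measured before and after treatment. It then says: "Classic models of change scores can be used where the baseline level can be controlled giving the so-called residual change score". Two advantages follow, the second being that "statistically each subject is started at the same point". The next step is that "our estimation model will be extended from the classic model of change scores to a repeated measures ANOVA (analysis of variance) or mixed model" for repeated measures. The text does not say whether the baseline value of the outcome is a covariate or one of the repeated outcomes in that model.

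Section 2.7 (Hypothesis 1a) expects depressed and control groups to differ before treatment. For IL-6 it cites "preliminary IL-6 data where the mean (SD) difference is 2.1 (3.6), with 80% power, two-tailed t-test at 5% significance level", and it gives preliminary group differences for connectivity, episodic memory and executive function. Section 2.2 has untreated controls return at week 6 for blood, MRI and neuropsychological testing. Under Hypothesis 2a, section 2.7 refers to non-specific change over time that the control group would also show.

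**The concern.** Adjusting for baseline puts groups on an equal footing when they are samples from one population, as randomised arms are. Depressed participants and controls are not. Each group regresses towards its own mean, so a depressed participant and a control with the same baseline IL-6 are expected to have different follow-up values even if neither group has changed. The adjusted comparison reports that gap as a difference in change (Lord's paradox).

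As worded, section 6.1 offers the method in the same paragraph that names case-control status as the only between-person factor. An analyst could reasonably apply it to depressed versus control, and the week 6 control data make that possible. The comparison with controls that is meant to separate treatment effects from repeat-testing and spontaneous change would then be biased for IL-6, cognition and connectivity.

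**Working it through.** **1. The plan's own figure.** Section 2.7 states: "an effect size (mean difference/SD) of at least .49 can be detected for a sample of 150 subjects, where 50 are controls". Check: (1.960 + 0.842) x sqrt(1/50 + 1/100) = 2.802 x 0.1732 = 0.485 (0.488 by the t distribution). Power at 0.49 is 80.8% (normal) or 80.3% (t). The figure reproduces, so the group sizes and test are as understood. The plan gives no figure for a residualised change analysis.

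**2. Inputs.**
- Group sizes: 100 depressed, 50 controls; two-sided 5% (section 2.7).
- Baseline gaps (section 2.7): IL-6 2.1/3.6 = 0.58 SD; episodic memory 1.44/2.96 = 0.49 SD; executive function 1.64/3.35 = 0.49 SD; amygdala-subgenual AC 0.23/0.17 = 1.35 SD; hippocampus-DLPFC 0.24/0.12 = 2.0 SD (absolute values).
- Pre-post correlation rho: .7 is the intraclass correlation that section 2.7 states for the connectivity interaction between treatment arms. Using it for other outcomes, and for depressed versus control, is an assumption. The range .5 to .9 is shown for IL-6.
- Attrition is ignored.

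**3. Formula.** Let each group's mean stay the same from baseline to week 6, with equal SDs and within-group slope rho. The baseline-adjusted group difference is then gap - rho x gap = (1 - rho) x gap, although true change is zero.

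**4. IL-6.** At rho .7: 0.3 x 2.1 = 0.63 units (0.63/3.6 = 0.175 SD). At rho .5: 1.05 units. At rho .9: 0.21 units.

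**5. Rejection rate for IL-6 at rho .7.** SE = 3.6 x sqrt(1 - .49) x sqrt(1/100 + 1/50 + 2.1²/(148 x 3.6²)) = 0.462; z = 0.63/0.462 = 1.36; probability of rejection about 28%.

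**6. Simulation.** 4,000 trials per setting, 100 versus 50, no true change in either group. ANCOVA adjusts for baseline with group in the model. The two-step method regresses follow-up on baseline in the pooled sample and compares residuals. Raw change is the group x time test with two time points. Results at rho .7:

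| Outcome (gap in SD) | Expected ANCOVA bias (SD) | ANCOVA rejects | Two-step rejects | Raw change rejects |
|---|---|---|---|---|
| IL-6 (0.58) | 0.175 | 27% | 25% | 4.7% |
| Memory, executive function (0.49) | 0.15 | 22% | 20% | 5.1% |
| Amygdala connectivity (1.35) | 0.41 | 78% | 65% | 5.3% |
| Hippocampal connectivity (2.0) | 0.60 | 94% | 78% | 4.3% |

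For IL-6, ANCOVA and two-step reject 47% and 44% at rho .5, and 11% and 9% at rho .9. Raw change stays between 4.3% and 5.7% in every setting.

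**7. Randomised arms.** With 50 versus 50 and no baseline gap, at rho .7, ANCOVA rejects 5.0% and two-step 4.8%, with bias near zero. Baseline adjustment is sound there.

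**8. Direction.** The artefact has the sign of the baseline gap. For IL-6, depressed participants look higher at week 6 than controls with the same baseline, which understates their normalisation.

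**The case against.** A reader might infer that the plan specifies a biased depressed-versus-control analysis. The documents do not support that.

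- The wording is permissive, and the text goes straight on to repeated measures ANOVA or a mixed model, which is free of this bias when baseline is an outcome.
- No listed hypothesis assigns residualised change to this contrast. In section 6.3, 1a is a baseline comparison, 1b and 1c are correlation or regression analyses without change scores, 2a compares randomised groups or pre with post, and 2b is confined to depressed subjects. Hypothesis 2c (section 1.1) is celecoxib versus placebo. The one explicit baseline-adjusted outcome is MADRS treatment response (sections 2.1 and 6.2).
- Where section 2.7 raises non-specific change, its method is a treatment group x time test between arms.
- Naming a single between-person factor is true of the design summary in 6.1 only. Sections 2.7 and 6.3, and the end of 6.1, compare randomised groups.

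All of this stands and makes the bias conditional. It does not close the gap. The mixed model is introduced as an extension of the change-score model, and how baseline enters is left open, so an analyst could follow the text and obtain either a biased or an unbiased depressed-versus-control result.

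A reader might also take the rejection rates as false support for Hypothesis 2. They would go against it, because the artefact makes normalisation look smaller. Nor is raw change safe for every outcome. Depressed participants enter with PHQ-8 of 10 or more (section 2.8) and controls with HAMD of 7 or less (section 5.2), so raw change in symptom scores can carry regression to the mean from selection.

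**Conclusion.** The concern holds in conditional form. The second stated advantage of residualised change is not an advantage for depressed versus control. If baseline-adjusted change were used for that contrast, IL-6 would show a spurious difference of about 0.63 units at rho .7 and a rejection rate of 25-28% in place of 5%. Over rho .5 to .9 the rate runs from about 45% down to about 10%. For connectivity at rho .7 it is about 65-94%, depending on the measure and on ANCOVA or two-step residuals.

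These figures rest on the preliminary baseline gaps in section 2.7, on an assumed rho, on equal SDs, and on group means that would be stable without treatment. The contrast between randomised arms is unaffected.

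**What to change.** In section 6.1:
- Name randomised arm as a between-person factor alongside depression status.
- Limit residualised or baseline-adjusted change to the randomised-arm contrast.
- State that any depressed-versus-control change in IL-6, cognition or connectivity is tested as group x time in the planned mixed model, with the baseline value as an outcome and not as a covariate.
- Delete the second advantage for the case-control factor.
- State the assumption that group means would be stable without treatment, and do not extend the rule to MADRS or HAMD.

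The cost is wording only. The mixed model is already planned and controls already have a week 6 visit, so no new data or visits are needed.

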### **1.1 *Introduction***

Major depression (MDD) is a cause of disability worldwide, but the etiology of MDD remains unclear. An emerging concept is that inflammation may have relevance, especially in MDD. We have data supporting increased inflammatory cytokines in MDD compared with controls that are associated with decreased hippocampus and amygdala volumes. MDD also had impairment in neuropsychological function in episodic memory, executive function, decreased hippocampus and amygdala resting state functional connectivity. Antidepressant treatment improved IL-6 levels, neuropsychological testing and resting state connectivity.

We will recruit patients with MDD (n = 100) and controls (n = 50) to characterize immune function, brain structure and connectivity and neuropsychological function. Using the Hospital of University of Pennsylvania's Pepper Lab we will measure participants' c-reactive protein (CRP) levels, and stratify participants according to CRP level (i.e. high (CRP  $\geq$ 3) and low (CRP  $<$ 3)). All participants with MDD (n=100), will receive a selective serotonin reuptake inhibitor (SSRI) antidepressant and we will randomize them to SSRI plus placebo (n $\leq$ 50) or SSRI + celecoxib (n $\leq$ 50). We will assess participants pre- and post-treatment with peripheral and central cytokine levels, neuropsychological tests and brain resting state functional connectivity.

Hypothesis 1: a) Compared with matched controls, MDD will have abnormalities in peripheral and inflammatory cytokines, neuropsychological function, hippocampal, amygdala and prefrontal cortex (PFC) structure and functional connectivity; b) Peripheral/central inflammatory cytokine levels will be associated with volume loss in hippocampus and amygdala; and c) Cumulative duration of depression will correlate with volume loss in hippocampus, amygdala, and PFC. d) Across the lifespan there will be an age effect interaction with depression.

Hypothesis 2: a) Once subjects have completed the antidepressant treatment, they will have greater normalization of IL-6 and IL-10, greater improvements in memory, executive function, and in resting state functional connectivity compared to their baseline measures; b) Improvement in clinical depressive scores will correlate with normalization of inflammatory cytokines; c) Those randomized to the addition of celecoxib (vs placebo) will have additive improvements in cytokines, resting state functional connectivity and depression scores.

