Hypothesis 1b: Cytokine levels will be correlated with hippocampal and amygdala volumes and PFC thickness; To examine correlational hypothesis 1b, we used a Fisher's r-to-Z transformation test for a correlation between IL-6 and volumetric measures. To achieve 80% power with a two-tailed Z test and 5% significance level, a correlation of |.23| can be detected for a sample of 150 subjects. Based on our preliminary data for IL-6 and for left CA2-3 we have a correlation of .33.

Aim 2: Characterize the effects of treatment on depression and the association with inflammation. Hypothesis 2a: Subjects randomized to treatment will have greater normalization of IL-6 and functional connectivity compared to those randomized initially to placebo. To achieve 80% power with a two-tailed t-test and 5% significance level, a mean difference of 2.1 can be detected with a standard deviation of 3.6 for a sample of 50 medicated and 50 nonmedicated subjects. Based on our preliminary data for IL-6, the mean (SD) difference, between the nonmedicated and medicated group for IL-6 is 2.7 (3.6). We will test Hypothesis 2a for improvement in functional connectivity with repeated measures ANOVA with the treatment group x time interaction result testing whether improvement in the outcome variables (increase in hippocampus and amygdala connectivity to DLPFC and AC) is greater in the treatment group than the placebo group, over and above non-specific changes over time (e.g., practice effects, naturalistic changes) that would be seen also in the control group. Our sample size of 100 with 50 in each group provides 80% power to detect a moderate effect size of .38 with .7 intraclass correlation on the group x time interaction, based on a two-tailed F-test with 5% significance level and assuming 10% attrition.

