variables such as neuropsychological measures and inflammatory markers. Generalized linear models (GLM) will be used for the baseline data. We are aware that numerous other confounders exist (such as age, race, education, statin use and gender). When a variable is identified to be related to the outcome and covariate of interest, i.e. confounder, we will adjust for it in the model of choice. A sensitivity analysis of statin and/or ARB use will be performed via analysis by statin and ARB use to determine if it is necessary to adjust or stratify by statin and ARB use. Models consider inclusion of the list of known covariates and their interaction. The importance of these models will be assessed through inspection of the change in the parameter of interest, as well as the parameter (and p-value) for the covariate. Point estimates, p-values, and confidence intervals to test the covariate of interest will be computed. Mixed model diagnostics and GLM diagnostics will be evaluated. For the continuous outcomes, we will assess if transformations exist that can bring about near normality. In addition, the impact of skew on the stability of estimates can be assessed using bootstrap methodology. For all models involving skewed predictors, we will assess the impact of the significant outliers using bootstrap and will check the linearity assumption. Other diagnostic procedures will be used to check for the validity of the GLM assumptions such as normality of the residuals and linearity assumption. Missing data problems are ubiquitous in aging research. Missing values can arise from several sources, (1) subjects are lost to follow-up, (2) missing CRFs, or (3) particular items of a CRF are skipped. We will employ multiple imputation. In this design, we have numerous indicators of outcome and predictors. The concern is that the possibility of a Type-I error is increased if a series of univariate tests is employed. Several solutions are possible in the context of this design: 1) use of Bonferroni Corrections or the less conservative extension to Bonferroni corrections 2) use of data reduction techniques like Principal Component Analysis (PCA) , and 3) use of multivariate mixed models. Based on the estimated numbers of remitters vs non-remitters we expect to enter approximately 53 subjects in Phase II. Using the estimates from Abbasi et al. (7) for serum IL-6 comparing SSRI+celecoxib to SSRI+placebo, we will have greater than 95% power by randomizing the 53 subjects between the two groups.

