Aim 2: Characterize the reversibility of brain dysfunction, including cognitive impairment with treatment of depression and its association with inflammation. Hypothesis 2a: Subjects randomized to treatment will have greater normalization of IL-6 and IL-10, greater improvements in memory, executive function and improvements in resting state functional connectivity compared to those randomized to placebo. For an unadjusted analysis, a paired t-test can be used to determine if there is a difference in the pre-treatment and post-treatment inflammatory cytokines. Mixed models will be utilized to assess if the inflammatory markers change over time adjusting for confounders. A mediator analysis will be utilized to determine whether MADRS has an effect independent of treatment on the inflammatory levels. The first

CONFIDENTIAL

approach would be to test for an interaction effect between baseline MADRS and treatment in a mixed model with inflammatory markers as the outcome adjusting for MADRS, treatment, and an interaction between MADRS and treatment. If the interaction term is not significant we will determine if MADRS independently of treatment or additively with treatment is related to inflammatory markers. Structural equation models can be an alternative approach for the mediator analysis.

Hypothesis 2b: Improvement in clinical depressive scores post treatment will be correlated with changes in cytokine levels. Change score models or joint mixed models will be utilized to assess the relationship between depression scores (outcome) and inflammatory markers, while adjusting for confounders in the depressed subjects.

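### Section 6.1 lets the data choose the covariates and does not exempt the randomised celecoxib comparison, so the arm model is open and can lose precision; fixing a short covariate list costs almost nothing

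*Combined protocol and SAP*

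**What the plan says.** Section 6.1 gives three data-driven routes to a covariate set.

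- A confounder rule: "When a variable is identified to be related to the outcome and covariate of interest, i.e. confounder, we will adjust for it".
- A model-comparison rule, covering models with the known covariates and their interactions: "The importance of these models will be assessed through inspection of the change in the parameter of interest", together with the covariate's own coefficient and p-value.
- A look at results by statin and ARB use, "to determine if it is necessary to adjust or stratify by statin and ARB use".

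No threshold or order of steps is given, and the list of confounders is open-ended.

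The randomised comparison is set out in Section 1.1: all depressed participants receive the SSRI and "we will randomize them to SSRI plus placebo" or SSRI plus celecoxib. Hypothesis 2c there concerns this contrast. Section 6.3 words Hypothesis 2a as an arm comparison as well ("Subjects randomized to treatment will have greater normalization of IL-6 and IL-10", compared with placebo), and specifies mixed models adjusted for confounders without listing them. Section 6.3 has no separate model for 2c.

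Some covariates are addressed. Sections 2.1 and 6.2 fix baseline MADRS as a covariate for post-treatment MADRS. For the other outcomes, Section 6.1 says only that baseline can be controlled. The CRP stratum, used to stratify depressed participants in Section 2.2, is not named as a model term anywhere in Section 6.

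**The concern.** A confounder search suits the case-control comparison, where depressed and control participants may differ systematically. In the celecoxib-placebo comparison any link between a baseline covariate and arm is chance, so there is no confounding to find. Two things follow if the Section 6.1 rules are used there. The confounder rule leaves out strongly prognostic covariates because randomisation has balanced them. And a rule that weighs models by how far the arm estimate moves, with no threshold, leaves open which model will be reported. The celecoxib effects on cytokines, connectivity and MADRS are the trial's only randomised answer. IL-6, the primary cytokine measure, is the most exposed, because its baseline is not firmly fixed as a covariate.

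**Working it through.** **Inputs.** From Section 2.7: an SD of 3.6, two groups of 50, and this target: "To achieve 80% power with a two-tailed t-test and 5% significance level, a mean difference of 2.1 can be detected". Attrition of 10% is stated there only for the group-by-time calculation ("assuming 10% attrition"); it gives 45 per arm. Candidate covariates: the five named in Section 6.1 (age, race, education, statin use, gender) plus ARB use. The documents give no R-squared for these covariates, so the values below are assumptions shown as a range. The 0.5 SD effect is also assumed.

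**1. The plan's own figure.** n per arm = 2(1.960 + 0.842)² × (3.6/2.1)² = 2 × 7.85 × 2.94 = 46.1, so 47; the t-test version gives 48. The planned 50 is consistent with this. Power by t-test is 82.3% at 50 per arm and 78.1% at 45.

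**2. How often the confounder rule admits a covariate.** Under randomisation the chance that a covariate appears related to arm is simply the threshold used. Of six covariates, at most 6 × 0.05 = 0.3 (p<.05) or 6 × 0.20 = 1.2 (p<.20) enter on average, and fewer once a relation to outcome is also required.

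**3. Power with k covariates fixed.** For effect d and n per arm, the noncentrality is d × √(n/2) × √(1 − k/(2n − 1)) / √(1 − R²), on 2n − 2 − k degrees of freedom. With d = 0.5 and n = 45:

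- no covariates: 0.5 × 4.743 = 2.372, power 65%;
- six covariates each correlated 0.15 with outcome (R² = 6 × 0.0225 = 0.135): 2.372 × 0.966/0.930 = 2.463, power 68%;
- six covariates each correlated 0.25 (R² = 6 × 0.0625 = 0.375): 2.372 × 0.966/0.791 = 2.897, power 82%.

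**4. The rules compared by simulation.**

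| Rule | 45 per arm, 0.5 SD, six covariates, R² 0.14 / 0.38 | 50 per arm, 2.1/3.6 SD, five covariates, R² 0.20 / 0.40 |
|---|---|---|
| Unadjusted | 65% | 82.3% / 82.3% |
| Related to outcome and arm | 65–67% | 83.1% / 85.2% |
| 10% change in estimate or covariate p<.05 | 69% / 80–81% | 88.1% / 94.8% |
| All covariates fixed | 68–69% / 82% | 88.6% / 95.2% |

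In the right-hand column the confounder rule keeps 0.8 of a possible 6.3 points (R² 0.20), or 2.9 of 12.9 (R² 0.40). The change-or-p-value rule gives up only 0.4 to 0.5 points there.

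**5. Type I error at nominal 5%.** Applied mechanically, the confounder rule gives 3–5%, a 10% change-in-estimate rule 3.9–5.0%, a covariate p-value rule 4.8–6.2%, and the combined change-or-p-value rule 5.0–6.0%. Monte Carlo error is about 0.6 points. All are near nominal.

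**6. Worst case.** Suppose the model reported is whichever subset of main effects gives the smallest arm p-value. With six candidates (64 subsets, 45 per arm) the false-positive rate is 11% at R² 0.14 and 17% at 0.38. With 50 per arm and R² of 0 / 0.2 / 0.4 it is 7.4% / 11.9% / 17.5% for five candidates and 6.7% / 13.7% / 19.5% for seven.

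**7. The short list proposed below.** Six covariates are the benchmark above, not the proposal. With CRP stratum, age and gender alone at the same assumed strengths, R² is 3 × 0.0225 = 0.0675 or 3 × 0.0625 = 0.1875. The step 3 formula gives 2.414 (67%) or 2.586 (72%). This omits the outcome's baseline value. No pre/post correlation is given for IL-6. If the 0.7 intraclass correlation that Section 2.7 uses for connectivity is borrowed as one, adjusting for baseline leaves 1 − 0.7² = 0.51 of the variance, against 2(1 − 0.7) = 0.60 for a change score.

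**The case against.** The strongest reply is that Section 6.1 is about the case-control contrast. It names case-control status as the single between-person factor. Section 6.3 repeats the confounder list only for Hypothesis 1a, and its adjusted mixed model for 2a concerns change over time. Section 1.1 also frames 2a as change from baseline. This shows that application to the arm effect is an inference, not an instruction. But Section 6.1 itself discusses power for SSRI plus celecoxib against SSRI plus placebo, Sections 2.7 and 6.3 word 2a as an arm comparison, and no other covariate rule is available for 2c. The gap stands.

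A reader might infer that the celecoxib p-value is invalid, with a false-positive rate of 11% or more. The documents do not support that. Nowhere do they say to choose a model on the arm's p-value, and the rules as written, applied mechanically, stay near 5%. A reader might also infer that nothing is fixed for the arm effect, or that precision is always lost. Baseline MADRS is fixed for one of the three outcome families, and the change and p-value criteria together keep most of the gain. The clear loss comes from the confounder sentence alone, and even there power is not below the unadjusted level; a gain is forgone.

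**Conclusion.** The point holds as a pre-specification gap with a modest, avoidable cost. Nothing keeps the data-driven covariate rules away from the randomised comparison. If the confounder rule is used there, power stays at about 65% where six prespecified covariates would give about 69% to 82% (45 per arm, 0.5 SD effect). Those figures rest on assumed covariate R² of 0.14 to 0.38; with weaker covariates the difference shrinks towards nothing. Mechanical use of the rules does not materially inflate type I error. The 11% to 19% range is a ceiling for unrestricted choice among subsets when R² is about 0.14 to 0.4. It describes what the absence of thresholds leaves possible, not what the plan prescribes. This is a cheap improvement, not a flaw that undermines the trial.

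**What to change.** Add to Section 6.1: *For every celecoxib-versus-placebo contrast the covariates are fixed before unblinding: the baseline value of the outcome, the CRP stratum, age and gender. None is added or dropped for its relation to arm, its p-value, or the change it makes in the arm effect. Any other covariate set for the arm effect is a labelled sensitivity analysis.*

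State that the confounder search and the statin/ARB step apply to the non-randomised analyses: Hypotheses 1a–1c, Hypothesis 2b, and pre/post change. Hypothesis 2b needs to stay on that list, because it relates two post-randomisation changes and can be confounded. The baseline value and CRP stratum are the natural choices: Section 6.1 itself argues for baseline control, and Section 1.2 says CRP correlates highly with cytokine levels.

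The cost is a few sentences, a few degrees of freedom, and less freedom to choose the model later. All the covariates are already collected. If they proved unrelated to outcome, the price would be small: with five useless covariates at 50 per arm, simulated power fell from 81.8% to 79.8%.
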